the anaesthesiologists in charge of the surgery. The anaesthesiologists, accessors, and patients will be blinded to the type of drug administered during surgery. The administered drug will be unmasked, with the agreement of the primary investigator, when esketamine-related severe adverse events occur (such as an allergy to the study drug) after the intervention and before the termination of surgery.

Outcomes

The primary outcome is the proportion of participants attaining remission (defined as a MADRS score less than or equal to 10) three days after surgery, based on an evaluation by blinded accessors at the bedside.

Secondary outcomes, including the differences in MADRS scores at three days and five days (or discharge) after surgery and the rates of patients achieving a response (MADRS scores reduced to or lower than half of the baseline MADRS score), the rate of severe pain within 72-hour postoperative period (severe pain is defined by the numeric rating scale pain scores equal to or more than 7).²¹

Safety outcomes include manic symptoms evaluated by the 11-item Young Mania Rating Scale (defined by YMRS scores more than or equal to 5) within the 3-day postoperative period,²² psychotic symptoms measured by a nonzero score on four particular items of the Brief Psychiatric Rating Scale (unusual thought content, suspiciousness, hallucinations, and conceptual disorganization) during the three days after surgery,^{23, 24} dissociative symptoms accessed by a nonzero score on the Clinician-Administered Dissociative States Scale within three days after the operation,²⁵ and all drug-related adverse events during surgery or before discharge.

Data management

The clinical data will be recorded and managed with the electronic database. The paper version materials including the protocol, the case reported forms, informed consent forms, and electronic version database will be preserved by the primary investigator and stored in the independently locked strongbox in Beijing Tiantan Hospital.

Sample size calculation

It has been reported that the remission rate difference in the antidepressant effects between esketamine and ketamine was 3.8% in treatment-resistant depression

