patients.²⁶ In the perioperative population with depressive symptoms, the remission rate was reported to be 23.1% in the ketamine group and 9.3% in the placebo group based on the PASSION study at our research site. We assumed that the remission rate in the esketamine group will be 19.3% and that in the placebo group will be 10%. A sample size of 506 participants will provide 80% power to show the difference between the esketamine group and the placebo group (with a ratio of 1:1), including 1 interim analysis by using a 2-sided significance level of 0.05.²⁷ With the consideration of a 10% attrition rate, the total sample size is planned to be 564.

Interim analysis

The planned interim analysis will be performed after 424 patients (75% of the total sample size) completed the follow-up. This interim analysis will be based on the ITT principle, and the P value will be set at 0.019 following adjustment by O'Brien-Fleming methods.²⁸

Statistical analysis

Continuous variables will be reported as the mean (standard deviation) for normally distributed data and the median (interquartile ranges) for skewed distributions. Categorical variables will be reported as the number (proportion), and the relative risk with its 95% confidence intervals will be calculated. The difference between groups will be reported with 95% confidence intervals of absolute differences calculated by independent t-tests for continuous variables and using the Hodges–Lehmann method for skewed variables. The primary endpoint of remission rate at 3 days after surgery will be analyzed by using the chi-square test or Fisher's exact test. The secondary outcomes will be analyzed using t-tests, Mann–Whitney U tests, and chi-square or Fisher's exact tests as appropriate. The adjusted odds ratios will be estimated by using a logistic regression model by taking into account the unbalanced baseline variables, age, sex, the severity of depressive symptoms, and pain severity after surgery.

For missing values, both imputations with the mean or median or the last observed assessment and multiple imputations will be applied. Sensitivity analysis for different imputation plans will be used to explore the statistical nature of the missing data. All statistical tests will be 2-sided at a significance level of 0.05 and the effect sizes will

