The null hypothesis of no difference in remission rate between the two arms of intervention will be analysed by a two-sided test at the 5% level of significance.

$$H_0: \lambda_1/\lambda_2 = 1$$

$$H_1: \lambda_1/\lambda_2 \neq 1$$

where λ_1 is the remission rate at postoperative day 3 in the group treated with esketamine and where λ_2 is the same timepoint in the group treated with placebo.

5. Sample size determination

The difference in the remission rates of antidepressant effects between esketamine and ketamine was reported to be 3.8% in patients with treatment-resistant depression. In the perioperative population with depressive symptoms, the remission rate was reported to be 23.1% in the ketamine group and 9.3% in the placebo group on the basis of the PASSION study at our research site. We assumed that the remission rate in the esketamine group would be 19.3% and that in the placebo group would be 10%.

A sample size of 506 participants provided 80% power to show the difference between the esketamine group and the placebo group (with a ratio of 1:1), including 1 interim analysis with a two-sided significance level of 0.05. Considering a 10% attrition rate, the total sample size is planned to be 564.

6. Interim analysis

The planned interim analysis will be performed after 424 patients (75% of the total sample size) have completed the follow-up. This interim analysis is based on the

intention-to-treat principle, and the p value is set at 0.019 following adjustment by the O'Brien-Fleming method. ^[6] The trial will be stopped after interim analysis if a significant difference between the groups is detected.

7. Population analysis

Total population

This population will comprise all the subjects screened and for whom a record exists in the study database. This population will be used for listing adverse events occurring prior to randomization and reasons for withdrawal occurring prior to randomization.

Modified Intent-to-Treat Population

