If the amount of missing data is lower than the prescribed attrition rate, which is 10%, the data will drop out. Missing data during the assessment period will be replaced with negative results before breaking blind. Sensitivity analysis will be applied for the different imputation methods, such as imputation with means or medians or dropouts or negative results. The missing data will be reported and analysed to determine their effects on primary efficacy.

9. Statistical analysis

General statistical calculations

For binary outcomes, the summary statistics are reported as the number and proportion, and the χ^2 test was used for hypothesis testing. For outcomes measured on a continuous scale, the summary statistics are reported as the mean and standard deviation (SD) or median and interquartile range (IQR) depending on normality according to the Shapiro-Wilk test. Statistical inference to evaluate the effect of

treatment was presented as absolute mean differences and 95% CIs via the independent t test and linear regression for continuous variables, except skewed variables, for which the absolute difference and 95% CIs were calculated via the Mann-Whitney U test and the Hodges-Lehmann method. All the summarized descriptive statistics will be presented to one further decimal place unless otherwise specified. P values are rounded to 3 decimal places (those less than 0.001 are displayed as <0.001).

Follow-up data

The CONSORT flow chart will be used to summarize the follow-up of patients throughout the trial. Each center records the details of all randomization, intervention, and missing data.

Demographic and baseline characteristics

The demographic information, such as age, sex, weight, height, and body mass index, will be summarized and presented to the participants in the two intervention groups. Other variables included education level, marital status, American Society of Anesthesiologists physical status classification, Charlson's comorbidity index, smoking history, and comorbidity history. Baseline data for operation characteristics, such as delayed extubation, type and extent of resection, and time to spontaneous respiration, will also be obtained.

Efficacy analyses

All statistical analyses for the main effects were two-sided at P values less than 0.05.

Primary efficacy analysis

The primary outcome was postoperative 3-day remission events assessed by the MADRS scale after intervention.

Main Model

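### At the planned remission rates, the imputation methods named in SAP section 8 add nothing to its two basic missing-data rules for the primary outcome, and the Protocol's multiple imputation is not carried over

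*SAP*

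**What the plan says.** The primary outcome in both documents is remission three days after surgery, "defined as a MADRS score less than or equal to 10" (Protocol, Outcomes). The sample-size sections of both documents assume 19.3% remission on esketamine and 10% on placebo.

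SAP section 8, Missing Data, gives two handling rules. Missing data are dropped if they amount to less than the 10% attrition allowance. It also states: "Missing data during the assessment period will be replaced with negative results before breaking blind". It then describes the sensitivity work: "Sensitivity analysis will be applied for the different imputation methods, such as imputation with means or medians or dropouts or negative results". No imputation model and no tipping-point or best/worst-case analysis is described, and the SAP does not mention multiple imputation.

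The Protocol (Statistical analysis) goes further: "For missing values, both imputations with the mean or median or the last observed assessment and multiple imputations will be applied". It gives no imputation model, variables or target. SAP section 1 says the SAP is to be used together with the Protocol. SAP section 7 adds a per-protocol analysis, described as a sensitivity analysis for the effect of missing data.

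**The concern.** A sensitivity analysis is informative only if it makes a different assumption about the unseen outcomes. Here the outcome is a yes/no cut of a score, and few patients are expected to fall on the yes side. A typical score filled in for a missing patient then falls on the no side, which is also what the negative-result rule does. Methods listed as different would return the same table, and a reader could take their agreement as evidence of robustness.

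The question left open is what happens if patients without a day-3 rating remitted at a different rate from those who were rated, especially if that difference is not the same in the two arms.

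**Working it through.** **Inputs from the documents.** Cut-off 10; remission 19.3% and 10%; entry MADRS of 22 or more; 506 evaluable, 10% attrition, 564 in total.

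**Assumptions.** The documents give no day-3 mean, SD or missing counts. I take 28 of 282 missing per arm (about 10%), planned rates among those observed, and SDs of 4 to 12.

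**1. The plan's sample size.** With mean rate 0.1465 and difference 0.093:

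n = [1.960√(2×0.1465×0.8535) + 0.842√(0.193×0.807 + 0.10×0.90)]² / 0.093² = 225.8 per arm.

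The continuity correction, (n/4)[1 + √(1 + 4/(0.093n))]², gives 246.8, so 247 per arm and 494 in total. At a final-look level of 0.044, which follows from an interim p of 0.019 at 75% information, the total is 512. The stated 506 lies between. Attrition: 253/0.9 = 281.1, rounded up to 282 per arm, or 564.

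**2. Median.** With remission below 50%, more than half the scores exceed 10, so the median does too. A median-imputed patient is a non-remitter, whatever the shape of the distribution.

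**3. Mean of the score.** Even if every remitter scored 0, a mean of 10 or less would need non-remitters, who score 11 or more, to average at most 10/0.807 = 12.4 on esketamine and 10/0.90 = 11.1 on placebo. That is implausible in patients entering at 22 or more. Under a normal shape, mean = 10.5 + z×SD, where z is the normal quantile at one minus the remission rate. This gives 14.0 to 20.9 on esketamine and 15.6 to 25.9 on placebo. A mean-imputed patient is a non-remitter.

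**4. Mean of the 0/1 outcome.** The SAP does not say whether the score or the yes/no outcome is imputed. The arm's mean would be 0.193 or 0.10. Rounded, that is non-remission; unrounded, it returns the complete-case proportion. A mean pooled over arms (74/508 = 0.146) rounds to non-remission; unrounded, it adds the same fraction to every missing patient in both arms, again without using patient information.

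**5. Last observation (Protocol only).** No MADRS is scheduled between baseline and day 3, so the carried value is normally the baseline score of 22 or more: non-remission again.

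**6. Results, Pearson chi-square without correction.** Observed remitters: 0.193×254 = 49 and 0.10×254 = 25.

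| Handling of missing patients | Esketamine | Placebo | RR | p |
|---|---|---|---|---|
| Dropped | 49/254 | 25/254 | 1.96 | 0.0025 |
| Negative, median, or mean score | 49/282 | 25/282 | 1.96 | 0.0028 |
| 0 esketamine, 7 placebo remit | 49/282 | 32/282 | 1.53 | 0.041 |
| 0 esketamine, 8 placebo remit | 49/282 | 33/282 | 1.48 | 0.056 |
| 0 esketamine, all 28 placebo remit | 49/282 | 53/282 | 0.92 | 0.66 |

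No method named in the SAP produces the last three rows. Eight of 28 is 29%, about three times the planned placebo rate. The tipping count is the same at a final-look level of 0.044, because p=0.041 still passes.

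For comparison, imputing at each arm's own rate adds about 5 (0.193×28) and 3 (0.10×28) remitters: 54/282 vs 28/282, RR 1.93.

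**7. Unequal missingness at about the planned rates.** With 40 missing on esketamine and 16 on placebo, dropping gives 47/242 vs 27/266 (RR 1.91, p=0.003) and negative gives 47/282 vs 27/282 (RR 1.74, p=0.013). With 16 and 40 missing, dropping gives 51/266 vs 24/242 (RR 1.93) and negative gives 51/282 vs 24/282 (RR 51/24 = 2.125).

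**The case against.** A reader might infer that the plan has no means of detecting missing-data bias. The documents do not support that. Step 7 shows the two rules separating when missingness differs by arm. With a smaller effect than planned they can even disagree on significance: with 14 missing on esketamine and 42 on placebo, 40/268 vs 24/240 gives p=0.095, while 40/282 vs 24/282 gives p=0.034. At about the planned rates the same pattern (52/268 vs 24/240, against 52/282 vs 24/282) gives p=0.003 and 0.0006, so nothing flips. This part of the objection stands. What remains is that neither rule lets a missing patient be a remitter, and with balanced counts the two rules give the same risk ratio.

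A reader might also infer that mean and median imputation force non-remission in all circumstances. They do not. The median result needs remission below 50%. The mean result needs a mean score above 10, which is highly plausible but not certain: remitters all at 0 and others all at 11 would give 0.807×11 = 8.9 and 0.90×11 = 9.9. Mean imputation of the 0/1 outcome can instead return the complete-case proportion.

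Nor can it be said that multiple imputation has been abandoned. The SAP's list is given as examples, and the Protocol, which the SAP says to use alongside it, commits to multiple imputation. Even so, a method that the later and more detailed document does not name, and for which neither document gives a model, is not prespecified in usable form.

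The per-protocol analysis removes protocol violators and imputes nothing, so it tests no assumption about unseen outcomes. Finally, the missing-data paragraph covers all endpoints, and mean or median imputation may have been meant for the continuous scales in Table 2. That is fair, and it is why the change should be confined to the primary outcome.

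**Conclusion.** The point holds in a limited form. At the planned rates, mean, median and negative-result imputation of the MADRS score give one and the same primary table, and the remaining named option is complete case. Both results are already the SAP's basic rules. The gap is outcome-dependent missingness with balanced counts, which no named method examines.

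The size is moderate. With about 10% missing per arm and the planned effect, the conclusion survives until 8 of 28 missing placebo patients remit and no missing esketamine patient does. With a smaller observed effect it is more fragile. At 44/254 vs 26/254, p is about 0.02, as it is with missing counted as negative (44/282 vs 26/282); three missing placebo remitters (44/282 vs 29/282) take it to 0.060.

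These figures rest on assumed missing counts, on one-sided assumptions about who remitted, and, in the last example, on an esketamine rate of 17.3%, below plan. They illustrate what would go unreported; they do not predict bias. This should be changed, but it does not invalidate the primary analysis.

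**What to change.** In SAP section 8, for the primary outcome only, replace mean and median imputation with two analyses:

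1. **Multiple imputation, as the Protocol promises, with the model written down.** Impute the day-3 MADRS score by arm from baseline MADRS, PHQ-9, severity stratum, age, sex and, where available, discharge MADRS. Classify each imputed score at 10 or less and combine with Rubin's rules.
2. **A tipping-point grid.** Vary the number of remitters among missing patients separately in each arm and report where the conclusion changes. Multiple imputation under missing-at-random would not by itself explore the lopsided patterns in the table, so both are needed.

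Keep complete case and missing-as-non-remission as the simple analyses.

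The cost is SAP wording and a few hours of programming. All the variables are already collected. The downside is that the result may look slightly less robust than several agreeing analyses would suggest.

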The intent-to-treat (ITT) population will include all the subjects after randomization and who received esketamine or placebo during surgery. After randomization, it is assumed that all participants have been administered a placebo or esketamine. The modified intent-to-treat population will be excluded from the analysis after randomization situations no longer meet the eligibility criteria, patients who do not have surgery, or patients who cannot undergo follow-up due to surgery-related complications, such as aphasia or coma. The modified ITT population will be tested for demographic characteristics and efficacy and safety outcomes. The population will be used for primary analysis of the efficacy and safety outcomes.

Per-Protocol population

The per protocol (PP) population will comprise all participants except subjects who are confirmed as protocol transgressors. The subjects excluded from the PP population will be confirmed before being blind. This population was used for sensitivity analysis to determine the effect of missing data. In the PP population, subjects will be analysed according to the treatment received and the real events after postoperative assessments.

8. Statistical considerations

The data will be analyzed by Stata 16.0 software (Stata Corp LP, College Station, TX,

USA) and all significance tests will be two-sided, with an alpha setting of 0.05 and 95% confidence intervals confirmed.

Subgroup analysis

The rate of postoperative 3-day remission will be presented at each level of the variables listed below. The degree of change in the treatment effect of each subgroup at different levels will be evaluated via an interaction test.

Multiplicity

The single primary outcome was defined in the protocol, and all other efficacy variables were treated as secondary or other. The only comparison of interest in this study was between esketamine and placebo, and there was no need to adjust for multiple comparisons. All estimates of treatment effects for secondary endpoints will be presented with 95% confidence intervals, no inferential tests will be performed, and only exploratory tests with simple descriptions of these endpoints will be performed.

Missing Data

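### The final primary test keeps p<0.05 after an efficacy look at p<0.019, so the overall two-sided type I error is about 5.5%, not the stated 5%

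*SAP*

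**What the plan says.** **Interim.** SAP section 6 states: "The planned interim analysis will be performed after 424 patients (75% of the total sample size) have completed the follow-up". The Protocol's Interim analysis section has the same timing, and both set p = 0.019 by the O'Brien-Fleming method. SAP section 6 adds: "The trial will be stopped after interim analysis if a significant difference between the groups is detected".

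**Design level.** SAP section 5 presents the sample size as "including 1 interim analysis with a two-sided significance level of 0.05". The Protocol's Sample size calculation says the same.

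**Final test.** Every level that reaches the final primary test is 0.05:
- SAP section 4: the primary null hypothesis "will be analysed by a two-sided test at the 5% level of significance".
- SAP section 8: an alpha of 0.05 and 95% confidence intervals for all significance tests.
- SAP section 9, Efficacy analyses: "All statistical analyses for the main effects were two-sided at P values less than 0.05".
- Protocol, Statistical analysis: "All statistical tests will be 2-sided at a significance level of 0.05".

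The Multiplicity paragraph of SAP section 8 says "there was no need to adjust for multiple comparisons" and does not mention the interim look. No section of either document gives a nominal level for the final analysis other than 0.05.

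**The concern.** An interim look that can stop the trial for a significant difference is a chance to reject the null hypothesis, so it uses part of the 5%. A group-sequential boundary therefore has a threshold for each look, and the final one must lie below 0.05. This plan writes down the interim threshold only and applies the full 0.05 at the end.

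The confirmatory claim on the single primary outcome depends on this rule. If the trial runs to completion and the p-value lies just under 0.05, an analyst following SAP section 9 would declare success. A reader applying the named O'Brien-Fleming method at 75% would not. If that is settled only after the p-value is known, the answer will not be credible.

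**Working it through.** **Inputs**
- Overall two-sided alpha 0.05, including one interim (SAP section 5).
- Interim at 424 patients, stated as 75% of 564, with p = 0.019 (SAP section 6).
- Final test at 0.05 (SAP sections 4, 8 and 9; Protocol, Statistical analysis).
- Remission 19.3% vs 10%; 506 evaluable, 253 per arm; 564 with 10% attrition (SAP section 5).

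**1. Reproduce the plan's 0.019.** Lan-DeMets O'Brien-Fleming-type spending with one-sided 0.025 on each side spends, per side, 2[1 − Φ(z₀.₀₁₂₅/√t)]. At t = 0.75, 2.2414/0.8660 = 2.588, so each side spends 2 × 0.00482 = 0.00965. Doubled, this is 0.0193, which matches the stated 0.019.

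**2. Find the final level that belongs with it.** Let Z₁ and Z₂ be the interim and final statistics. Under the null they are bivariate normal with correlation √t. Solve

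1 − P(|Z₁| < c₁, |Z₂| < c₂) = 0.05 for c₂.

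| Boundary, t = 0.75 | Interim p | Final p |
|---|---|---|
| Lan-DeMets O'Brien-Fleming, one-sided 0.025 doubled | 0.0193 | 0.0442 (z = 2.012) |
| Classical O'Brien-Fleming | 0.0200 | 0.0439 |
| Lan-DeMets on two-sided 0.05 | 0.0236 | 0.0416 |
| Interim fixed at the plan's 0.019 | 0.0190 | 0.0444 (z = 2.010) |

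None of these variants allows 0.05 at the end.

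**3. Type I error of the plan as written.** Put c₁ = 2.3455 (p = 0.019) and c₂ = 1.960 (p = 0.05) into the same formula.
- t = 0.75: overall alpha = **0.0550**. The interim uses 0.0190 and the final look adds 0.0550 − 0.0190 = 0.0360, where only 0.05 − 0.019 = 0.031 is available. The relative excess is 0.0050/0.05 = 10%.
- t = 424/506 = 0.838: overall alpha = **0.0529**. This applies if all 424 count at the interim and only 506 are evaluable at the end. With the interim kept at 0.019, the allowed final level is then 0.0468. If the spending is recomputed at that fraction, the pair is 0.0287 and 0.0418.

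**4. Check with the planned test.** Two-look uncorrected chi-square tests were simulated with 3 million trials per setting. The null remission rates were 10% and the average of the two assumed rates, (19.3% + 10%)/2 = 14.65%.

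| Per arm, interim then final | Null rate | Final at 0.05 | Final at 0.0444 |
|---|---|---|---|
| 212, 282 | 10% | 0.0552 | 0.0495 |
| 212, 282 | 14.65% | 0.0553 | 0.0502 |
| 212, 253 | 10% | 0.0523 | 0.0484 |
| 212, 253 | 14.65% | 0.0535 | 0.0486 |

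**5. A result in the gap.** Take 40 vs 25 remissions at 253 per arm. The proportions are 0.1581 and 0.0988, and the pooled proportion is 65/506 = 0.1285. Then z = 0.0593/√(2 × 0.1285 × 0.8715/253) = 1.993 and p = 0.0463. This passes 0.05 and fails 0.0444.

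**6. Power with the corrected level.** At 253 per arm, 19.3% vs 10%, t = 0.75 and interim 0.019, lowering the final level from 0.05 to 0.0444 changes power from 85.2% to 84.1% (unpooled variance), or from 84.6% to 83.5% (pooled variance).

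**The case against.** The best defence is that 0.05 is the overall level. The sample size sections say it includes the interim, O'Brien-Fleming has a paired final boundary, and so the final threshold may be implied and merely unwritten. That fits SAP section 5. It does not fit section 9, which applies P<0.05 to the main-effect analyses without exception, or section 8, which sets 0.05 for all significance tests.

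Four narrower points have some force.
- The multiplicity sentence follows a statement that there is only one treatment comparison. It is most naturally about endpoints and arms, so it is not evidence that the authors rejected an interim adjustment. It does leave the repeated look unaddressed.
- The 84% fraction is only one reading. If 10% attrition applies at both looks (382/506), or if missing assessments count as non-remission so that all 564 contribute, the fraction is about 75%.
- The 40 vs 25 example depends on that fraction. Its p of 0.0463 fails at 75% (0.0444) and fails if spending is recomputed at 84% (0.0418). It passes if 0.019 is kept at 84% (0.0468). Fisher's exact test, which the SAP also allows, gives 0.062, although with counts this large the uncorrected chi-square is the natural choice.
- The inflation is 0.3 to 0.5 percentage points and affects the conclusion only in a narrow band of final p-values.

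These points limit the size of the problem and make the exact final level conditional on the information fraction. None of them brings the plan as written back to 5%.

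**Conclusion.** The concern holds. With an efficacy stop at p<0.019 and a final test at p<0.05, the overall two-sided type I error is 0.0550 at the documents' own 75% information and 0.0529 at 84%, against the claimed 0.05. At 75%, a final p-value between about 0.044 and 0.05 would be wrongly declared positive.

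The calculation assumes that the interim stop is applied as SAP section 6 states, that the two test statistics have the usual correlation √t, and that the interim and final analysis sets are nested. The interim is described as intention-to-treat and the primary analysis as modified intention-to-treat. This could shift the correlation slightly but does not remove the inflation. The result does not depend on how the 506 was derived.

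The excess is modest. It still needs correcting before unblinding, because it sits in the decision rule of the only confirmatory test.

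**What to change.** - **SAP sections 4, 6 and 9, and the Protocol's Interim analysis and Statistical analysis sections:** state the final nominal two-sided level for the primary outcome next to the 0.019. At 75% information it is about 0.044 (0.0442 with the exact spending boundary, 0.0444 with the interim fixed at 0.019). Name the spending function.
- **Information fraction:** define it, with its denominator, and state that the final level is recomputed from the fraction actually observed. If the interim look has already been made at 0.019, keep that as the alpha spent and solve for the final level at the actual fraction (for example 0.0468 at 84%).
- **Confidence interval:** report the primary effect with a matching level, 95.6% when the final level is 0.044. SAP section 8 currently fixes 95%.
- **SAP section 8, Multiplicity:** limit the no-adjustment statement to the absence of other primary comparisons, and refer to the interim adjustment.

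The cost is wording in both documents and about one percentage point of power (85.2% to 84.1% unpooled, 84.6% to 83.5% pooled), still above the stated 80%. No patients are added.
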